#### AP 10-701

AP 10-701, previously referred to as Gluco-Pyranosylphospho-Lipid A Aqueous Formulation (GLA-AF), is a TLR-4 agonist. Point-of-injection formulations with this immunostimulant will be prepared immediately prior to vaccination by adding an appropriate volume of AP 10-701 to Na-GST-1/Alhydrogel® and withdrawing an appropriate volume to administer the desired amount of Na-GST-1/Alhydrogel® plus 5mcg AP 10-701.

#### CPG 10104

CPG 10104 is a TLR-9 agonist. Point-of-injection formulations with this immunostimulant will be prepared immediately prior to vaccination by adding an appropriate volume of CPG 10104 to Na-GST-1/Alhydrogel® and withdrawing an appropriate volume to administer the desired amount of Na-GST-1/Alhydrogel® plus 500mcg CPG 10104.

## **Normal Saline, 0.9% Sodium Chloride**

Normal saline will be used as the placebo. It consists of a sterile 0.9% physiologic solution of sodium chloride that has no pharmacologic activity.

### **6.1.1 Acquisition**

Na-GST-1/Alhydrogel® for this study will be supplied to the study site by the Baylor College of Medicine. Vials of CpG 10104 and AP 10-701 will be purchased from the Infectious Diseases Research Institute (IDRI).

Normal saline (0.9% sodium chloride injection, USP) and albendazole will be purchased commercially by the GWU Investigational Drug Service.

The *Necator americanus* Larval Inoculum that will be used for CHHI in this study will be supplied by the Department of Microbiology, Immunology, and Tropical Medicine of GWU under a current Investigational New Drug application to the US FDA (IND#015752). Briefly, *N. americanus* eggs will be obtained from the feces of chronically infected human volunteers who are subjects in a GWU IRB-approved clinical trial of CHHI (NCT#01940757). These individuals are regularly tested to ensure that they are negative for HIV, HBV, and HCV. Fecal material is processed following a qualified standard procedure, and after hatching from eggs, the *N. americanus* larvae are stored in the dark at ambient temperature (19-25°C) until use. Controls for the manufacturing process are tests for viability (motility), species identification, and microbial bioburden of the larvae. Donors are tested for HIV, HBV, and HCV prior to release of each new batch of larvae and release will not be accepted if any of these tests are positive.

Na-GST-1/Alhydrogel®, CpG 10104, AP 10-701, and the sterile saline placebo will be transported to the Investigational Drug Service at GWU MFA at 0.5°C to 10°C; temperature recording devices will accompany the vaccines at all times during transport to ensure temperature limits have not been violated.

### **6.1.2 Formulation, Packaging, and Labeling**

#### **6.1.2.1 Na-GST-1/Alhydrogel®**

Na-GST-1/Alhydrogel® is supplied as a sterile milky-white suspension (when shaken slightly). Each 2.0 ml vial contains 1.35 ml of a 0.1 mg/ml suspension of Na-GST-1 adsorbed to 0.8 mg/ml of Alhydrogel® in a buffer consisting of 10% glucose and 10 mM imidazole, pH 7.4. Glucose acts as an excipient and imidazole as the buffer based on evidence that these components specifically enhance the stability and solubility of Na-GST-1. The dose that will be administered in this study is 100 µg of Na-GST-1, or 1.0 ml of the final drug product. This volume contains the equivalent of approximately 400µg aluminum. Na-GST-1/Alhydrogel® was manufactured, formulated and vailed at Walter Reed Army Institute of Research.

#### **6.1.2.2 CpG 10104**

CpG 10104 will be supplied as a clear to slightly hazy, colorless aqueous solution at a concentration of 2mg/mL, in multi-dose vials containing 0.8 ml each. Appropriate volumes of

CpG 10104 will be withdrawn and added to a vial containing Na-GST-1/Alhydrogel® (as described in the study Pharmacy Manual). The mixture must be administered not more than 4 hours after mixing the CpG 10104 with Na-GST-1/Alhydrogel®. CpG 10104 has been manufactured according to cGMP by the Infectious Diseases Research Institute (IDRI).

#### **6.1.2.3     *Glucopyranosyl-Lipid A Aqueous Formulation (AP 10-701)***

AP 10-701 will be supplied as a 0.5 mL clear to slightly hazy, colorless aqueous solution in multi-dose vials containing 25 µg/mL of GLA without preservative. Appropriate volumes of AP 10-701 will be withdrawn from the multi-dose vials using a syringe and added to a vial containing Na-GST-1/Alhydrogel® (described in the Investigator's Brochure and study Pharmacy Manual). The mixture must be administered not more than 24 hours after mixing the AP 10-701 with Na-GST-1/Alhydrogel®. AP 10-701 has been manufactured according to cGMP by the Infectious Diseases Research Institute (IDRI).

#### **6.1.2.4     *Placebo (Normal Saline, 0.9% Sodium Chloride, USP)***

Normal saline (0.9% sodium chloride injection, USP) is a sterile, nonpyrogenic, isotonic solution. Each mL contains sodium chloride 9 mg and contains no preservatives, bacteriostatic, antimicrobial agent, or added buffer. The solution may contain hydrochloric acid and/or sodium hydroxide for pH adjustment (pH 5.3, range 4.5-7.0).

#### **6.1.2.5     *N. americanus Larval Inoculum***

*N. americanus* larval inoculum will be supplied as a clear, colorless suspension in individual cryotube vials containing 50 infectious *N. americanus* larvae each in sterile water.

### **6.1.3    Product Storage and Stability**

The vaccine, CpG, and AP 10-701 will be stored at the site in a refrigerator at 2°C to 8°C until just prior to administration and will not be frozen. Normal saline placebo will be stored at the site at room temperature (20°C to 25°C). All study product vials will be stored in the upright position.

*N. americanus* Larval Inoculum will be maintained at 19°C to 25°C until just prior to administration.

## **6.2    Dosage, Preparation and Administration of Study Intervention/Investigational Product**

Doses of Na-GST-1/Alhydrogel® administered without AP 10-701 or CpG 10104 will be prepared the site Investigational Pharmacist by withdrawing appropriate volumes into syringes of appropriate size. Study product doses will be prepared using aseptic technique in a biosafety cabinet. The Na-GST-1/Alhydrogel® plus AP 10-701 formulation will be prepared by adding appropriate volume of AP 10-701 solution to vials of Na-GST-1/Alhydrogel® within 24 hours of vaccination. The Na-GST-1/Alhydrogel® plus CpG formulation will be prepared by adding appropriate volume of CpG solution to vials of Na-GST-1/Alhydrogel® within 4 hours of vaccination. Doses of the sterile saline control will be prepared by withdrawing the appropriate volume into syringes of appropriate size.

Doses of vaccine/placebo will be administered by qualified study personnel in the deltoid muscle of the appropriate arm after disinfecting the skin with an alcohol swab and allowing it to dry.

Individual doses of *N. americanus* larvae will be prepared at MITM and transported to the study site at ambient temperature, immediately prior to application on a study subject's skin. Doses of the *N. americanus* larval inoculum will be prepared by pipetting the entire contents of the dose vial containing 50 motile larvae onto a sterile absorbent pad under a fume hood. The absorbent pad will then be directly applied to the subject's forearm and immobilized there using a transparent sterile adhesive dressing for at least one hour before removing and placing the pad back into the dose vial for counting of residual larvae at MITM.

### **6.3 Modification of Study Intervention/Investigational Product for a Subject**

There will be no dose modifications. If a subject's second and/or third dose of study vaccination or CHHI is deferred, it should be rescheduled to occur within the acceptable protocol-specified window for that visit. If this period elapses, the site must obtain prior approval from the Sponsor to administer the second and/or third study vaccination, or the CHHI, and the documentation of approval should be filed in the subject's chart. Subjects who do not receive the second and/or third study vaccination or CHHI will be asked to return for safety assessments and for scheduled venous blood sample collections for immunogenicity testing and will be followed for the duration of the study.

Unblinding can occur upon request of the Independent Safety Monitor or the SMC at any time during the study.

### **6.4 Accountability Procedures for the Study Intervention/Investigational Product(s)**

Study vaccine, AP 10-701, CpG 10104 and sterile saline placebo supplies must be received by a designated person at the GWU MFA Investigational Drug Service pharmacy, handled and stored safely and properly, and kept in a secure location to which only the designated individuals have access. Study-site personnel are responsible for maintaining accurate records of the vaccine supplies (i.e., Na-GST-1/Alhydrogel®, the sterile saline placebo, CpG10104, and AP 10-701) received, the quantities administered to study subjects, and the amounts remaining at the conclusion of the study.

After administration of vaccine or AP 10-701 or CpG 10104 doses, the empty or wasted vials will be accounted for and stored at the study site until monitoring by the study Sponsor or their designee. At the conclusion of the study, all used and unused Na-GST-1/Alhydrogel®, CpG 10104, and AP 10-701 vials will be returned to the Sponsor or destroyed on site upon direction from the Sponsor, or maintained at 2 to 8°C until further notice from the Sponsor regarding their disposition.

Supplies of *N. americanus* larval inoculum will be prepared and stored at the Department of MITM at GWU. Individual doses of larvae will be prepared on the planned day of inoculation and

transported to the study clinic for administration to study subjects. At the study clinic, the larval doses must be received by a designated person, handled and stored safely and properly and kept in a secure location prior to administration. MITM personnel will be responsible for maintaining accurate records of the supplies of the *N. americanus* larval inoculum, the quantities administered to study subjects, and the amounts remaining at the conclusion of the study

## **6.5 Assessment of Subject Compliance with Study Intervention/Investigational Product**

Not Applicable.

## **6.6 Concomitant Medications/Treatments**

Administration of any medications, therapies, or vaccines will be recorded on the appropriate data collection form. Concomitant medications will include all medications taken within the 30 days prior to enrollment, 28 days after each dose of study vaccine, from study Day 140 to 297, and for new-onset chronic medical conditions through the end of participation in the study for each subject. Prescription and over-the-counter drugs will be included as well as vitamins and supplements.

Use of new medication will prompt an evaluation for the presence of a new diagnosis of chronic medical disease or chronic medical condition.

Medications that might interfere with the evaluation of the investigational vaccine formulations should not be used unless absolutely necessary. Medications in this category include, but are not limited to, glucocorticoids, i.e., high dose oral, parenteral and daily inhaled steroids, and immunosuppressive or cytotoxic drugs. Other than from participation in this study, subjects should not receive experimental agents, including vaccines, for the duration of the study.

The administration of licensed vaccines, should be delayed until 28 days after the last administration of investigational vaccine, with the exception of the inactivated influenza vaccine that should not be administered within 2 weeks of receipt of study vaccine (i.e., 2 weeks prior to planned study vaccination and 2 weeks after study vaccination).

## 7 STUDY SCHEDULE

The following sections provide a detailed listing of the procedures and studies to be performed in this protocol at designated time points. The total volume of blood (approximately 1091 mL) to be collected from each volunteer over 14 months is less than the volume collected when donating three units of blood and should not compromise the health of trial subjects.

See **Appendix A** for the schedule of study procedures.

### 7.1 Screening

Volunteers aged 18-45 years, inclusive, will be invited to undergo screening for the study. During this initial screening visit, a member of the study team will review the consent form with the volunteer. The study team member will explain the study to the volunteer and will clarify all of the volunteer's questions. Volunteers will be encouraged to ask questions. The volunteer may either sign the consent form immediately or later after further consideration.

The following procedures will be performed upon initial screening (note that all procedures might not be performed on the same day):

1. Explain the study and Informed Consent to the volunteer.
2. Elicit a complete medical history, including medication history, and for female subjects, a menstrual and contraceptive history and/or history of surgical sterility.
3. Administer a complete physical examination.
4. Obtain blood for hematology, biochemistry, anti-dsDNA, rheumatoid factor, serum ferritin, and tests for HIV and viral hepatitis (B and C).
5. Obtain urine for urine dipstick testing for glucose and protein, as well as urine pregnancy testing in females.
6. Counsel females to avoid becoming pregnant during the study.
7. Obtain feces for fecal occult blood testing and baseline parasitology.
  - Volunteers unable to provide a fecal sample during the screening visit may provide a sample prior to the planned Day 0 study visit. A fecal sample must be obtained prior to determination of eligibility and larval administration.
  - Explain procedures for fecal sample collection, storage, and transport to the clinic.
8. Explain the procedure for at-home fecal sample collection, storage, and transport to the clinic on or before Day 0.

Screening steps 2-8 must be performed within 90 days of the planned enrollment into the study. Should this screening window be exceeded before the first vaccination, screening procedures (not including administration of the informed consent form) may be repeated to ensure continued eligibility for the study (blood screening tests can be repeated a maximum of one time for this reason). Abnormal screening test results may be repeated to confirm the result, at the discretion of the investigator.

## 7.2 Enrollment/Baseline

Volunteers will not be considered enrolled in the study until they have received their first dose of vaccine. In the event that a volunteer is randomized but not enrolled on the day of first vaccination, they will be replaced with an eligible alternate.

### Study Day 0 (Visit #1: Day of First Vaccination)

1. Verify that Informed Consent was obtained.
2. Verify that all applicable eligibility criteria have been met.
3. Perform abbreviated history (including concomitant medications) and physical exam, focusing on any acute complaints.
4. Obtain blood for hematology, biochemistry, rheumatoid factor, anti-dsDNA, anti-Na-GST-1 antibody and cellular immunology assays.
5. For females, obtain a urine sample for pregnancy testing. Test must be negative to proceed; a positive test will exclude the volunteer from the trial.
6. Record vital signs (blood pressure, oral temperature, and heart rate). Vital signs recorded pre-vaccination on Day 0 will be considered as baseline.
7. Subjects will be enrolled and randomly assigned to a study group by the vaccine manager prior to the first study vaccination.
8. Administer the vaccine in the deltoid muscle. Record the site of injection (i.e., right or left arm) on the appropriate data collection form.
9. Observe for at least 1 hour after vaccination to evaluate for immediate adverse reactions. During the 1-hour post-immunization wait period, study staff will discuss signs and symptoms of potential AEs, describe proper use of digital thermometers, injection-site reaction measurement tools, and subject symptom diaries.
10. Record vital signs at the end of the 1-hour post-immunization wait period.

## 7.3 Follow-up

### Study Day 3 (Visit #2) – Telephone Call

1. Review interim medical history emphasizing any acute signs or symptoms (including entries on the post vaccination symptom memory aid).
2. Collect concomitant medication information.

### Study Day 7 (Visit #3)

1. Perform basic history and physical exam (including injection site), emphasizing examination of any acute complaints.
2. Record vital signs (oral temperature, pulse, and blood pressure).
3. Review and collect subject post vaccination symptom memory aid.
4. Obtain blood for cell-mediated immunity (CMI) assays.

### Study Day 14 (Visit #4)

1. Perform basic history and physical exam (including injection site), emphasizing examination of any acute complaints.
2. Record vital signs (oral temperature, pulse, and blood pressure).
3. Review and collect subject post vaccination symptom memory aid (if not collected on Visit #3/Study Day 7).

4. Obtain blood for hematology, biochemistry, rheumatoid factor, anti-dsDNA, anti-Na-GST-1 antibody and CMI assays.

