3. Collect prior week's weekly GI symptom memory aid and give new weekly GI symptom memory aid.
4. Obtain fecal sample for parasitological testing.

Study Day 189 (Visit #21)

1. Perform basic history and physical exam, emphasizing examination of any acute complaints.
2. Record vital signs.
3. Obtain fecal sample for parasitological testing.
4. Collect prior week's weekly GI symptom memory aid and give new weekly GI symptom memory aid.
5. Obtain blood for hematology, antibody and cellular assays.

Study Day 196 (Visit #22) – Telephone Call

1. Review interim medical history emphasizing any acute signs or symptoms (including entries on the GI symptom memory aid).
2. Collect concomitant medication information.

Study Day 203 (Visit #23)

1. Perform basic history and physical exam, emphasizing examination of any acute complaints.
2. Record vital signs.
3. Obtain fecal sample for parasitological testing.
4. Collect prior week's weekly GI symptom memory aid and give new weekly GI symptom memory aid.
5. Obtain blood for hematology.

Study Day 210 (Visit #24) - Telephone Call

1. Review interim medical history emphasizing any acute signs or symptoms (including entries on the GI symptom memory aid).
2. Collect concomitant medication information.

Study Day 217 (Visit #25)

1. Perform basic history and physical exam, emphasizing examination of any acute complaints.
2. Record vital signs.
3. Obtain fecal sample for parasitological testing.
4. Collect prior weeks' GI symptom memory aids and give two new weekly GI symptom memory aids.
5. Obtain blood for hematology.

Study Day 224 (Visit #26) - Telephone Call

1. Review interim medical history emphasizing any acute signs or symptoms (including entries on the GI symptom memory aid).
2. Collect concomitant medication information.

Study Day 231 (Visit #27)

1. Perform basic history and physical exam, emphasizing examination of any acute complaints.
2. Record vital signs.
3. Obtain fecal sample for parasitological testing.
4. Collect prior weeks' GI symptom memory aids and give two new weekly GI symptom memory aids.

5. Obtain blood for hematology, antibody and cellular assays.

Study Day 238 (Visit #28) - Telephone Call

1. Review interim medical history emphasizing any acute signs or symptoms (including entries on the GI symptom memory aid).
2. Collect concomitant medication information.

Study Day 245 (Visit #29)

1. Perform basic history and physical exam, emphasizing examination of any acute complaints.

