## 8 STUDY PROCEDURES/EVALUATIONS

### 8.1 Clinical Evaluations

Subjects will be monitored for local and systemic adverse events during specific protocol-defined periods. As with other aluminum hydroxide-adsorbed vaccines, hypersensitivity reactions would be expected to occur within the first 24 hours after vaccination, and other severe local or systemic reactions within 72 hours of vaccination. Subjects will therefore be observed for immediate reactions following each vaccination for at least 1 hour, and will have a clinical assessment at the study clinic on Days 7 and 14 following each vaccination. A telephone call with the subject will take place on Days 3 and 28 following vaccinations 1 and 2 to monitor for adverse events. Day 28 following vaccination 3 falls on the day of CHHI and the subject will be assessed at the study clinic. Should a subject call on a study clinician to report an adverse event (AE), it will be fully documented in their study chart, and discussed with the Principal Investigator.

Following CHHI, local larval application site reactions are expected to occur within the first month after application of the larvae. Subjects will therefore be observed for immediate reactions following each larval application for at least 1 hour. Subjects will have a telephone call on day 3 following CHHI to monitor for adverse events. A clinical assessment at the study clinic will be performed on Days 7 and 14 following CHHI. Gastrointestinal AEs are expected to occur after approximately week 4 after CHHI; subjects will therefore be evaluated weekly from weeks 5 through 20 after CHHI, until treatment with albendazole.

All AEs will be graded for severity and relationship to study vaccine or larval application, captured on the appropriate case report form (CRF), and followed to resolution. All Serious Adverse Events (SAEs) will be reviewed by a study physician, recorded on the appropriate SAE form, reported according to applicable regulations and guidelines, and followed through to resolution or stabilization by a study clinician. Special attention will also be paid to monitoring for the occurrence of Adverse Events of Special Interest (AESIs), which include inflammatory and autoimmune disorders that may potentially be related to the use of an immunostimulatory adjuvant, and gastrointestinal, hematologic or respiratory disorders that may potentially be related to CHHI.

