## 9 ASSESSMENT OF SAFETY

### 9.1 Specification of Safety Parameters

Safety will be assessed by the frequency and severity of:

1. Study product (vaccine or CHHI)-related serious adverse events occurring from the time of the first study vaccination through approximately 10 months after the last study vaccination.
2. Study vaccine-related solicited Adverse Events – reactogenicity events occurring on the day of each study vaccination through 14 days after each study vaccination:
  - a) Injection site reactions including erythema (redness), induration (hardness)/swelling, pain, and tenderness.
  - b) Systemic reactions including fever, myalgia (body aches/muscular pain exclusive of the injection site), arthralgia (joint pain exclusive of the injection site), headache, nausea, and vomiting.
3. CHHI-related solicited adverse events – reactogenicity events occurring on the day of CHHI through study Day 280 (time of treatment with first dose of albendazole):
  - a) Application site reactions including pruritus, rash, induration (hardness)/swelling, pain, and tenderness.
  - b) Gastrointestinal reactions including abdominal pain, abdominal bloating, flatulence, nausea, vomiting, and diarrhea.
  - c) Respiratory reactions (possibly due to migration of larvae through the lungs) including cough and sore throat.
4. Clinical safety laboratory adverse events occurring throughout the study. Parameters to be evaluated include WBC, ANC, absolute eosinophil count, hemoglobin concentration, and platelet count; ALT; creatinine; rheumatoid factor; and, anti-ds DNA antibodies.
5. Unsolicited Adverse Events – non-serious adverse events occurring from the time of each study vaccination through approximately 28 days after each vaccination and from study Day 140 (day of CHHI) through Day 297.
6. New-onset chronic medical conditions occurring from the time of the first study vaccination through approximately 10 months after the last study vaccination.
7. Adverse Events of Special Interest occurring from the time of the first study vaccination through approximately 10 months after the last study vaccination.

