### 9.2.2 Vaccine Reactogenicity

All subjects will be observed for at least 60 minutes after each study vaccination to detect and treat any immediate AEs. Subjects will also complete study memory aids after each vaccination beginning with the day of vaccination and through 14 days after vaccination. Injection site reactions including bruising, redness, induration (hardness)/swelling, pain, and tenderness will be recorded on the study aids. Systemic reactions including fever, myalgia (body aches/muscular pains exclusive of the injection site), arthralgia (joint pains exclusive of the injection site), headache, nausea, and vomiting will also be recorded.

Subjects will also be asked to record any medications taken and any emergency room or healthcare provider visits (other than routine check-ups). The subject memory aid will be reviewed with the subject at subsequent clinic visits.

Vaccine reactogenicity events are AEs that are known to occur with types of vaccine similar in composition to those being tested in this study. The following Toxicity Grading Scales will be used to grade solicited local (injection site) and systemic (subjective and quantitative) reactions:

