### 9.2.3 CHHI Reactogenicity

All subjects will be observed for at least 60 minutes after application of the *N. americanus* larvae during CHHI to detect and treat any immediate AEs. Subjects will also complete study memory aids after CHHI beginning with the day of larval application and through Day 280 when they will be treated with albendazole to cure their infections. For the first 4 weeks after application of the *N. americanus* Larval Inoculum, the memory aids will be used to record pruritus, pain, tenderness, rash and swelling at the site of larval application, as well as cough and sore throat (to capture symptoms that may possibly be related to larval migration through the lungs). Starting on Day 175 (approximately 5 weeks after CHHI) of the study until the participant receives their first dose of albendazole, the memory aids will be used to record nausea, vomiting, diarrhea, abdominal pain, abdominal bloating and flatulence. Female participants of childbearing potential will additionally capture on the memory aids the form of contraception they are using. The memory aids will include a printed reminder of the potential risks associated with use of albendazole during pregnancy.

Subjects will also be asked to record any medications taken and any emergency room or healthcare provider visits (other than routine check-ups) through Day 297. The subject memory aid will be reviewed with the subject at subsequent clinic visits.

CHHI reactogenicity events are AEs that are known to occur with hookworm infection. The following Toxicity Grading Scales will be used to grade solicited local (larval application site) and systemic (subjective and quantitative) reactions:

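### The memory-aid steps in Protocol 7.3 do not cover the solicited-event windows: about Days 8-14 after each dose, and up to 3 of 20 weeks after CHHI, have no diary if the visit lists are followed

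*Protocol*

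**What the plan says.** **Vaccination phase.** Protocol 3.2.1 (Safety, item 1) counts solicited reactions from the day of each vaccination through 14 days. Protocol 9.2.2 makes the diary the source: "Subjects will also complete study memory aids after each vaccination beginning with the day of vaccination and through 14 days after vaccination". In Protocol 7.3, the Day 7 list says "Review and collect subject post vaccination symptom memory aid", with no condition and no re-issue. The Day 14 list says "Review and collect subject post vaccination symptom memory aid (if not collected on Visit #3/Study Day 7"). Doses 2 and 3 follow the same pattern (Days 63 and 70; Days 119 and 126). SAP 5.7.5.2 tabulates solicited events by day after each vaccination.

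**CHHI phase.** Protocol 9.1, item 3, defines the solicited events, GI reactions included, as "reactogenicity events occurring on the day of CHHI through study Day 280". Protocol 9.2.3 has diaries run from larval application to Day 280. It assigns site and respiratory items to the first 4 weeks and begins GI items as follows: "Starting on Day 175 (approximately 5 weeks after CHHI) of the study until the participant receives their first dose of albendazole". Protocol 8.1 states "Gastrointestinal AEs are expected to occur after approximately week 4 after CHHI", and Protocol 2.1.9.1 reports onset at roughly 4 to 6 weeks in the site's earlier CHHI study. In Protocol 7.3, Day 154 hands out two weekly aids, with the next clinic visit on Day 175. Days 182, 189 and 203 each say "Collect prior week's weekly GI symptom memory aid and give new weekly GI symptom memory aid". From Day 217 to Day 259, two aids are given for each two-week interval.

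**The concern.** The outcome definitions and the visit instructions describe different data. A coordinator who works from Protocol 7.3 takes the aid back halfway through the vaccination window. The same coordinator issues too few weekly sheets for some of the post-CHHI intervals.

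Two consequences follow. First, solicited events on uncovered days are likely to be under-recorded, and their daily severity is not captured prospectively. Second, the SAP's missing-data rules (SAP 5.1) deal only with partial dates. Nothing in the SAP separates a day on which no diary was held from a day on which the subject reported no symptom, and the by-day tables depend on that distinction.

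For GI reactions, the route of capture could also change the grade. An event handled as unsolicited is graded by Protocol Table 2. That table has no row for abdominal pain, bloating, flatulence, nausea or vomiting, and it starts Grade 1 diarrhea at 3 loose stools. Table 3, for solicited events, starts it at 2-3.

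**Working it through.** The check is a day-by-day count of which window days are covered by an aid in the subject's hands, using nominal visit days.

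**Stated figures.** The post-CHHI window is 280 - 140 = 140 days = 20 weeks. The GI diary starts at 175 - 140 = 35 days = 5 weeks. Both agree with Protocol 9.2.3. SAP 5.7.5.3 calls Day 175 about 4 weeks after CHHI, which does not agree.

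**Vaccination phase.** Days 0 to 14 give 15 diary days per dose. The collection visits fall at 7 - 0, 63 - 56 and 119 - 112, which is 7 days after each dose. If the entry for the collection day itself counts as made, an aid collected on day c holds c + 1 daily entries, so 15 - (c + 1) days are uncovered:
- c = 7: 15 - 8 = 7 days (Days 8-14), or 47% of diary days
- c = 5 (early edge of the ±2-day window): 15 - 6 = 9 days
- c = 9 (late edge): 15 - 10 = 5 days

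**CHHI phase.** The first aid is taken to cover Days 140-153, because it is collected on Day 154. Each weekly aid is taken to cover the 7 days from issue, up to the next clinic visit.

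| Issued on Day | Weekly aids | Next clinic visit | Weeks to cover | Uncovered |
|---|---|---|---|---|
| 154 | 2 | 175 | 3 | Days 168-174 |
| 175 | 1 | 182 | 1 | none |
| 182 | 1 | 189 | 1 | none |
| 189 | 1 | 203 | 2 | Days 196-202 |
| 203 | 1 | 217 | 2 | Days 210-216 |
| 217, 231, 245, 259 | 2 each | 14 days later | 2 each | none |
| 273 | 1 | 280 | 1 | none |

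Read literally, 21 days are uncovered, so 140 - 21 = 119 days (17 of 20 weeks) are covered. Within the GI-diary period, Days 175 to 280 are 15 weeks, of which 2 are uncovered. If two aids were meant on Day 203, 14 days are uncovered and 140 - 14 = 126 days (18 of 20 weeks) are covered. The position of the gap inside Days 189-203 depends on which week the subject fills in; the count does not.

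**GI onset.** Weeks 4 to 6 after Day 140 are Days 168-181, which is 14 days. The first 7 are uncovered and the last 7 are covered. This gap does not rest on the hand-out count alone: Protocol 9.2.3 itself ends site and respiratory items at 4 weeks (Day 168) and starts GI items at Day 175.

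**The case against.** The strongest reply is that Section 7.3 is loosely worded and that Section 9.2 governs. Protocol 9.2.2 uses the plural for memory aids and has them reviewed at later clinic visits. The hand-out after vaccination is not itemised, so one aid per dose is an inference. The Day 14 clause allows for an aid that was not collected on Day 7, and the Day 28 and Day 84 telephone calls still refer to aid entries. The Day 14 visit includes a history and an injection-site examination. These points stand in part. A reader might infer that all data for Days 8-14 are lost; the documents do not support that, because recall remains possible. What recall cannot supply is daily graded entries.

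On size, 47% of diary days is not 47% of reactions. Protocol 4 and 8.1 expect hypersensitivity within 24 hours and other severe reactions within 72 hours, inside the covered days. The same rule applies to all four blinded groups. A reader might also infer that the SAP tables will show no events on Days 8-14. That is a prediction, and the list of tables is held in a separate document.

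For CHHI, the Day 217 list collects the prior weeks' aids in the plural, which suggests that two were intended on Day 203. A firm count of three missing weeks is therefore too strong. The Day 189-203 gap is better supported, because Day 203 collects a single prior week's aid. The calls on Days 196 and 210 review aid entries but issue no new aid.

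Finally, it is tempting to say that GI events are unsolicited for the first five weeks. Protocol 9.1 classes them as solicited from the day of CHHI, Protocol 7.6 allows solicited-event review at unscheduled visits between Days 140 and 280, and the Day 175 visit takes a history. What is missing is a diary item, and only the week of Days 168-174 falls within the stated onset period.

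**Conclusion.** The conflict between Protocol 7.3 and Protocol 3.2.1, 9.1, 9.2.2 and 9.2.3 is real and should be corrected. If the aid is collected at Days 7, 63 and 119 as instructed, about Days 8-14 after each dose have no diary: 7 of 15 days, range 5 to 9. After CHHI, up to 3 of 20 weeks have none. Days 168-174 and one week of Days 189-203 are the firmer gaps; one week of Days 203-217 is possible but may be a drafting slip. GI reactions are defined as solicited from Day 140 but have no diary items before Day 175.

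The consequence is under-ascertainment in every arm, not an obvious bias between arms. How many reactions would be missed cannot be derived from the documents. The counts assume nominal visit days after CHHI, one week of coverage per weekly aid, and no further hand-outs described elsewhere, such as in the Manual of Procedures, which is not among the documents.

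**What to change.** In Protocol 7.3:
- At Days 7, 63 and 119, review the aid and leave it with the subject. Collect it at Days 14, 70 and 126.
- At Day 154, give a third weekly aid that carries GI items for Days 168-174.
- At Days 189 and 203, give two weekly GI aids, as is already done from Day 217.

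Reconcile Protocol 9.1 (item 3) and 9.2.3 on when GI items start, and correct the SAP's description of Day 175 from about 4 to about 5 weeks after CHHI.

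In the SAP, define days without a diary as missing, not as no event, in the by-day solicited tables, and show the number of subjects with a diary on each day. This step is useful even for data already collected.

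With these changes, coverage becomes 15 of 15 days per dose and 119 + 3 × 7 = 140 of 140 days after CHHI. The cost is revised visit wording, three extra weekly sheets per subject and one SAP rule. No visits are added.
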